**Plaque Regression and Progenitor Cell Mobilization with
Intensive Lipid Elimination Regimen
(PREMIER)**

Version 2.4 (Pivotal Study)

June 22, 2016

Principal Investigator:

[name]

Dallas VAMC

1. Rationale

1(a) Background

The most intensive pharmacologic lipid lowering therapy with statins, though proven superior to standard dose regimens, is still associated with an unacceptably high rate of recurrent cardiovascular (CV) events early after an acute coronary syndrome (ACS). Progression or rupture of lipid rich necrotic core (NC) elements of atherosclerotic vulnerable plaque (VP) leads to a majority of recurrent CV events. Vascular healing by endothelial progenitor cells (EPC) plays a crucial role in repair following ischemic injury primarily by endothelialization of VP and neovascularization of ischemic myocardium. In fact, EPC mobilization while on statin therapy has been shown to enhance coronary blood flow in patients with stable coronary artery disease (CAD), and reduce myocardial ischemia and CV events in patients with ACS within a few weeks of treatment. This has prompted a continuous drive towards lowering of total cholesterol and specifically low-density lipoprotein (LDL). However, what still remains uncertain is whether the most intensive LDL-lowering therapy (ILLT) with LDL-apheresis could lead to a rapid and detectable reduction in VP atheroma volume, along with a more robust EPC mobilization compared to standard statin therapy in ACS patients.

1(b) Hypothesis

We hypothesize that in ACS patients undergoing percutaneous coronary intervention (PCI), ILLT with LDL-apheresis plus statin therapy will significantly reduce the total atheroma volume of VP and augment mobilization of peripherally circulating endothelial progenitor cell colony forming units (EPC-CFU/ml), compared to guideline based standard statin monotherapy alone (SMT). We also hypothesize that the total number of and the percentage of patients with major peri-PCI procedure adverse events will not be a safety concern for the study.

1(c) Specific Objectives

This is the second phase of a multi-center trial of ACS patients. The first phase was a safety study involving 31 patients and was completed in December 2012. US Food and Drug Administration (FDA) reviewed the safety and efficacy data from the first phase and approved proceeding to this phase. In this trial, 128 participants will be randomized in a 1:1 ratio to either initial LDL-apheresis and an oral daily dose of 40-80mg of Atorvastatin or equivalent (ILLT group) vs. a daily dose of 40-80mg of Atorvastatin or equivalent without LDL-apheresis (SMT group) following an uncomplicated PCI. Intravascular ultrasound with virtual histology (IVUS-VH) derived coronary atheroma volume and composition will be obtained at baseline and 90 days after enrollment, while peripheral blood sampling will be performed at enrollment, and at 24 hours, 30 days, and 90 days post-PCI, along with a four-month and a six-month clinical follow-up visits to determine whether the ILLT group will affect:

1. The total number of and percentage of patients with major peri-PCI procedure adverse events (primary safety endpoint)

2. The total number of and percentage of patients with statin-related abnormal liver function test events and statin-related muscle injury events (secondary safety endpoint)
3. The total atheroma volume within a ≥ 20 mm long segment of the target coronary artery at 90 days IVUS-VH follow-up (primary effectiveness endpoint)
4. The %NC component within a ≥ 20 mm long segment of the target coronary artery at 90 days IVUS-VH follow-up (secondary effectiveness endpoint)
5. The EPC-CFU/ml of peripheral blood, compared to SMT group from baseline to 30 days and 90 days post-PCI (secondary effectiveness endpoint)
6. The major adverse CV events (MACE) at 90 days and at six months follow-up (secondary effectiveness endpoint)

2. Background and Significance

2(a) Background

2(a)(i). Lowering blood cholesterol with statins is well established as a long-term strategy to reduce death and ischemic CV events in patients with stable CAD¹⁻³. Major mechanisms by which lipid lowering is thought to improve outcome include preventing the development of new atherosclerotic lesions and stabilizing existing atherosclerotic plaques⁴. In addition, statins can reduce vascular inflammation⁵, decrease platelet aggregability and thrombus deposition⁶, and increase endothelium-derived nitric oxide production⁷. Most recently, statins have been reported to promote the neovascularization of ischemic tissue in normocholesterolemic animals by up regulating EPC mobilization and differentiation⁸.

[figure not shown]
2(a)(ii). Aggressive lipid lowering pharmacotherapy with statins, though proven superior to standard dose regimens, still is associated with an unacceptably high rate of recurrent CV events (28.8%)^{1,9}. Moreover, intensive statin regimens are significantly underutilized (5%) in ACS patients undergoing PCI, who are at highest risk for recurrent ischemic events¹⁰. ACS patients, who survive through the presentation, have a high rate of recurrent ischemic events, early after an index event³. This has prompted a continuous drive towards lowering of LDL goals.

2(a)(iii). Current analysis of statin studies also cannot definitively determine whether the benefit seen with high-dose statins is because of the high statin dose used or because low LDL levels are achieved. Our study will provide crucial information in this area by comparing ILLT which achieves a rapid drop in LDL levels using initial LDL-apheresis, followed with 40-80mg daily Atorvastatin or equivalent to SMT with 40-80mg daily Atorvastatin or equivalent. This has particular relevance in the context of our recent publication that showed ACS patients lack the ability to mobilize EPC in response to an endovascular injury¹¹. Thus, up-regulation of EPC mobilization with ILLT in ACS patients may define a novel mechanism (**Figure 1**) and therapeutic strategy to improve neovascularization of ischemic myocardium, and endothelialization of VP and endovascular stent prosthesis, especially drug-eluting stents. Circulating EPC levels also correlate to CV risks and predict CV events¹².

2(a)(iv). Clinical studies like the Myocardial Ischemia Reduction with Aggressive Cholesterol Lowering (MIRACL) trial have demonstrated that intensive cholesterol lowering with Atorvastatin administered immediately after hospitalization for ACS rapidly reduced the incidence of recurrent ischemic events over the first 16 weeks¹³. The Pravastatin or Atorvastatin Evaluation and Infection Therapy–Thrombolysis in Myocardial Infarction 22 (PROVE IT–TIMI 22) trial demonstrated that among patients who have recently had an ACS, an intensive lipid-lowering statin regimen provides greater protection against death or major CV events than does a standard regimen⁹. It showed a 16% reduction in the hazard ratio favoring intensive therapy. These early clinical benefits have been accompanied by only modest changes in intra-coronary plaque burden and are thought to be due to the atheroprotective property of mobilized EPC^{14,15}. This early effect of statin treatment on clinical endpoints can be partly

explained by a 1.5-fold increase in the number of circulating EPC within one week after initiation of statin treatment, followed by sustained increased levels to three-fold throughout the four-week study period in patients with stable CAD¹⁶. There are currently no studies of EPC mobilization in ACS patients with intensive lipid lowering therapy.

Figure 1: Proposed Study Mechanism

2(a)(v). Coronary atherosclerosis imaging: Although trials using clinical endpoints are the gold standard for evaluating novel atherosclerosis treatments, they are lengthy and resource-intensive. Surrogate endpoints, such as coronary angiography and IVUS-VH, allow a more cost-effective evaluation of novel treatments. IVUS-VH is a novel technology which allows for the identification of discrete plaque components using radiofrequency backscatter data¹⁷. IVUS can visualize the coronary artery wall and measure atherosclerosis volume. The reliability and reproducibility of total atheroma volume by traditional grey scale IVUS have been well validated, and we have published the first report on reproducibility of repeated IVUS-VH measurements in a clinical practice setting³². We reported excellent agreement between the two pullback measurements for lumen area vessel area and plaque burden. The Spearman rank-order correlation coefficients were (0.96, 0.96, and 0.95) for lumen area, vessel area, and plaque burden, respectively. (The data are presented in section 3(d) under "Work Accomplished").

IVUS has already been used as an endpoint in long-term trials (REVERSAL, or Reversal of Atherosclerosis with Aggressive Lipid Lowering¹⁸ and ASTEROID, or Study to Evaluate the Effect of Rosuvastatin on Intravascular Ultrasound-Derived Coronary

Atheroma Burden¹⁹) and in short-term IVUS follow-up trials with Apo-A1 Milano²⁰ and delipidated high density lipoprotein (HDL) treatments²¹. Currently there are two clinical studies that have evaluated early (≤ 12 week) IVUS derived coronary atheroma regression and have demonstrated significant regression from baseline with pre-beta HDL²¹ and ApoA-1 Milano²⁰ infusions. The change in atheroma volume in the control arm was 2.8mm^3 (increase) and that in the treatment arms were -12.18mm^3 and -14.1mm^3 with pre-beta HDL and ApoA-1 Milano therapies respectively. We also expect a robust response to ILLT with LDL-apheresis at 90 days. Our estimates of effect have been described in detail in Section 4(g) under "Biostatistical Considerations."

2(a)(vi). Endothelial progenitor cells play a crucial role in repair following ischemic injury²². This is achieved primarily by neovascularization and endothelialization of vulnerable atherosclerotic plaque. Thus, augmentation of circulating EPC in the setting of an ACS may significantly contribute to endothelialization of coronary VP, and limit myocardial ischemic injury²². Increasing the number of circulating EPC by transplantation of hematopoietic stem cells or by injection of in vitro differentiated EPC has been shown to improve neovascularization of ischemic hind limbs²³, accelerate blood flow in diabetic mice²⁴, and improve cardiac function²⁵. Therefore, augmentation of circulating EPC in the setting of an ACS may significantly contribute to the stimulation of neovascularization after tissue ischemia. Recently, EPC mobilization with statin therapy has not only been shown to rapidly enhance coronary blood flow in patients with stable coronary artery disease²⁶, but also to reduce myocardial ischemia in patients with ACS within a few weeks of treatment²⁷, along with a significant increase in circulating EPC. The current studies however, cannot definitively determine whether the EPC mobilization seen with statins is because of the statin dose used or the degree of LDL reduction achieved.

2(a)(vii). LDL-apheresis is an extracorporeal blood processing system to acutely remove LDL-cholesterol from the plasma²⁸. The approved LIPOSORBER[®] system will be used for the study. It contains dextran sulfate cellulose beads that selectively bind Apo-B containing lipoproteins (Lp(a), LDL and VLDL). During this procedure, plasma is separated from whole blood, LDL cholesterol removed from the plasma, and plasma and blood cells are recombined and returned to the patient²⁸. LDL-apheresis treatment can lower LDL cholesterol levels by 85% after a single treatment. In familial hyperlipidemia (FH) patients, this significant lowering of the LDL cholesterol level is not maintained due to a metabolic defect that causes the overproduction of LDL cholesterol. The LDL cholesterol level begins to increase (or rebound) after treatment, eventually returning to baseline in about one to three weeks, requiring recurrent treatments²⁸. We do not expect non-FH ACS patients to rebound rapidly, especially on continued statin therapy. We therefore propose using only one initial treatment with LDL-apheresis to achieve a rapid reduction in LDL-cholesterol, with follow-up guideline based lipid lowering pharmacotherapy with statins.

LIPOSORBER[®] treatment is very selective in removing LDL cholesterol, and does not affect HDL and triglyceride (TG) levels. A mean reduction in plasma proteins (15%), fibrinogen (29%), and platelets (5%) may be observed and rarely pose a risk to the patient^{28,29}. Approximately 300,000 treatments with the LIPOSORBER[®] system

have been performed worldwide on over 2,500 patients. Possible adverse reactions include hypotension, nausea/vomiting, flushing, chest pain, fainting, lightheadedness, anemia, abdominal discomfort, numbness/tingling, tachycardia, headache, shortness of breath, hemolysis, bradycardia, itching/hives, bleeding (due to the use of unfractionated heparin) and chills²⁸. Hypotension is the most common, and in US trials, occurred in <1% of all treatments and was treated effectively with intravenous fluids. If an ACE (angiotensin converting enzyme)-inhibitor is used to manage the patient's blood pressure; it should be held 36 hours prior to LDL-apheresis.

A single treatment with LDL-apheresis has been demonstrated to have significant effect on arterial blood flow. Tamai et al. demonstrated that a single LDL-apheresis treatment increased nitrous oxide production and forearm blood flow²⁹. A single treatment with LDL-apheresis has also been shown to significantly reduce modified LDL particle, remnant-like particle-cholesterol, and C-reactive protein³⁰. In the LACMART study, one LDL-apheresis treatment over one year lowered the LDL of FH patients aggressively and demonstrated a significant reduction in the plaque area and increase in the minimum luminal diameter (MLD) with an annual angiographic and IVUS follow-up³¹. It also demonstrated that the benefits of LDL-apheresis are substantial when used in the setting of a statin pharmacotherapy. It is important to point out that in the FH population, the LDL cholesterol level in the medication-only arm did not change significantly from baseline ($174\pm 39\text{mg/dl}$ to $181\pm 53\text{mg/dl}$), and with LDL-apheresis it decreased from $213\pm 25\text{mg/dl}$ to $140\pm 27\text{mg/dl}$, which is much higher than the expected post-LDL-apheresis LDL levels expected in non-FH ACS patients. The details of atheroma regression are described in section 4(g), "Biostatistical Considerations".

Thus, we believe that the proposed ILLT strategy to jumpstart aggressive LDL reduction post-ACS is expected to have significant pathophysiologic and biochemical effects, in addition to significant atheroma regression expected with nearly 85% reduction in serum LDL levels. Though the vasoactive effects of LDL-apheresis are well known, its effect on EPC mobilization has never been studied. Our proposal will for the first time test this hypothesis and lay the foundation for a dedicated mechanistic study in the near future.

2(b) Relevance to Veterans Health

We believe that our proposed strategy would provide the basis for a large-scale study to evaluate clinical endpoints as a primary objective and ultimately lead to the development of a new strategy to attain more aggressive therapeutic lipid goals, and reduce CV events post-ACS, reduce the socioeconomic burden of ischemic heart disease, and improve the quality of life of our veterans.

3. Work Accomplished

This proposal is a logical extension of our ongoing work. We have:

[figure not shown]
- i. Reported for the first time, failure of ACS patients to mobilize EPC in response to PCI in contrast to those with stable coronary lesions who demonstrate a robust EPC response to endovascular injury
- ii. Successfully isolated and identified EPC-CFU from peripheral blood samples of patients undergoing PCI
- iii. Performed LDL-apheresis in patients with CAD
- iv. Performed and reported IVUS-VH validation study to detect coronary atheroma volume and its components
- v. Demonstrated clinical trial experience by completing and publishing the SOS (Stenting of Saphenous vein graft) multi-center randomized trial with 12-month angiographic and IVUS follow-up

3(a) EPC Study in ACS

We have reported that EPC levels rise in response to PCI in patients with stable coronary lesions. In contrast, patients with unstable coronary lesions or ACS failed to mobilize EPC in response to PCI (**Figure 2**).

These data, the first in humans undergoing PCI, are consistent with a protective role for EPC mobilization. In this study, we investigated the effect of a discrete endovascular insult on human EPC recruitment into the peripheral circulation¹¹. By focusing on a defined clinical procedure, we were able to compare EPC levels before, and early after the manipulation at reproducible time points, avoiding possible nonspecific perturbations.

Figure 2: Baseline EPC levels and mobilization after PCI

(a) Baseline (pre-catheterization) EPC levels from patients with acute coronary syndrome (PCI_{ACS}-group), elective percutaneous coronary intervention (PCI_{Elect}-group), and normal epicardial coronary artery (control) patient groups. Baseline EPC-CFU levels were not different between groups ($P > 0.05$). EPC-CFU in PCI_{Elect} group (b) and PCI_{ACS} group (c) are shown before (PRE, squares) and after (POST, triangles) PCI. EPC-CFU levels increased in the PCI_{Elect} ($P = 0.0009$) but not in the PCI_{ACS} ($P = 0.20$) group. Circles are group means with S.E.M.

[figure not shown]
3(b) EPC Isolation

We have successfully isolated and identified EPC from peripheral blood samples of patients undergoing PCI using:

- i. Cell culture technique (**Figure 3**)
- ii. Flow-cytometry (**Figure 4**)

[figure not shown]
3(b)(i). EPC assay, using the cell culture method: EPC form typical colony forming units morphologically, and transform into cobblestone monolayer after 2-3 weeks (**Figure 3a-b**). Surface markers characteristic for EPC are von Willebrand Factor (vWF+), CD31+, CD34±, CD45- (**Figure 3c-f**)¹¹.

Figure 3 (a-f): Confirmation of EPC-CFU phenotype by cell culture

3(b)(ii). Using flow cytometry, we have also measured and confirmed isolated EPC in peripheral blood samples. The results of such an analysis in two patients recently performed in our laboratory are shown below (**Figure 4**), and demonstrate CD34+, CD133+, and CD45 weakly+ circulating EPC, similar to those identified by cell culture technique (purple) (unpublished data).

Figure 4: Circulating EPC Levels by Flow Cytometry

3(c) LDL-apheresis in Patients with CAD

[figure not shown]
Our group, under the directorship of [name] (Director LDL-apheresis center, University of Texas Southwestern Medical Center, Dallas, TX), has performed 12 uneventful LDL-apheresis sessions in two patients with CAD. One patient underwent LDL-apheresis every week, and the second every two weeks. Average reduction of LDL was approximately 84% after each session. Both patients have also been maintained on low dose statin therapy.

From our experience in the first phase of the PREMIER trial, there was one transient hypotension episode recorded in 20 patients randomized to LDL-apheresis after PCI for ACS. The event resolved spontaneously and was attributed to micturition.

3(d) Identification of Coronary Atheroma with IVUS-VH in ACS Patients undergoing PCI

The principal investigators (PI's) perform over 2,300 cardiac catheterizations and 500 coronary interventions annually, of which >80% are IVUS-VH guided. Coronary angiographic image acquisition, quantitative coronary angiographic analysis (QCA) using the Phillips proprietary software is performed by the PI's. The quantitative IVUS-VH image acquisition, live measurements of vessel diameter, cross-sectional area, plaque volume, and plaque composition assessments (QIVUS) are made by the PI's³². **Figure 5** demonstrates typical QIVUS assessments and measurements made during a typical study. These procedures can be performed reproducibly and safely by the PI's. The overall annual complication rate of our cardiac catheterization laboratory is 1.6%, of which 85% consist primarily of minor access site complications.

[figure not shown]

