ACS is defined as chest discomfort lasting at least 10 min within the last 24h, new ≥ 1 mm ST-wave or dynamic T-wave changes in at least two contiguous EKG leads but without significant ST elevation, and/or troponin I or T levels above the 99th percentile. Abnormal LFT is defined as any liver transaminases (ALT or AST) ≥ 3 times the upper limit of the normal laboratory reference. Atorvastatin 40-80mg will be considered equivalent to 20-40mg of Rosuvastatin. Patients on Simvastatin at the time of enrollment will be switched to Atorvastatin 40-80 mg or Rosuvastatin 20-40 mg.

After PCI of the target or culprit coronary artery (as determined by the operator) and IVUS-VH analysis of a ≥ 20 mm segment of the target coronary artery are performed during the index hospitalization for the qualifying ACS event, the patients will be randomized to ILLT or SMT if they meet all inclusion and exclusion criteria (**Figure 7, blue arrow**). PCI will be performed using standard technique at the discretion of the operator. 40-80mg daily Atorvastatin or equivalent treatments (ILLT or SMT) will be initiated within 24 hours after randomization. Patients randomized to the ILLT arm will undergo LDL-apheresis within 36 hours after presentation unless the 36-hour window is mandatory for those who were on ACE inhibitors to allow for the complete washout of ACE inhibitors. Adjunctive anti-platelet and anti-thrombin therapies will be at the discretion of the primary operator and clinical team. Refer to **Figure 8** for all study timelines.

4(c)(ii). Inclusion Criteria:

- (1). Willing and able to provide informed consent (including HIPAA)
- (2). Age > 30 years

- (3). Presenting with acute coronary syndrome (ACS), manifested as unstable angina or non-ST-elevation myocardial infarction
- (4). Referred for clinically indicated, non-emergent (the procedure is not required to be performed within 3 hours after patient presentation) coronary angiography and PCI with IVUS-VH of target coronary artery for ACS
- (5). Successful placement of two large-bore IV cannulas in bilateral upper extremities
- (6). Fasting (≥ 12 hrs) LDL ≥ 70 mg/dl while on ≤ 80 mg Atorvastatin or equivalent dose of other statin, performed at time of admission

4(c)(iii). Exclusion Criteria:

- (1). Known allergy to aspirin, statins, or iodinated contrast
- (2). Positive pregnancy test, planning to become pregnant, or breast-feeding

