- (2). The EPC-CFU/ml of peripheral blood assessed at various time points (pre-PCI, post-PCI, 30 days of follow-up, and 90 days of follow-up) will be analyzed via Mixed Linear models with random intercepts. The treatment effect, time effect and their interaction will be considered with or without

adjusting for age, pre-existing CAD, pre-existing diabetes, baseline LDL levels, and other relevant covariates such as ACS, peripheral vascular disease, and chronic kidney disease. The statistical test of interest is the time by treatment interaction.

- (3). Contrasts will be used in the Mixed Linear models to compare the differences among any specifically interested time points.

4(g)(vi). Statistical Analysis of Safety Endpoints and Complications: The primary safety endpoints, the secondary safety endpoints, and the incidence of major adverse cardiovascular endpoints (MACE) including death, myocardial infarction, coronary revascularization, and stroke will be analyzed in two ways. For each type of event, the percentage of people who experience the event at least once will be compared using the chi-square test. Logistic regression models will be performed to adjust for the covariates such as age, pre-existing CAD, and pre-existing diabetes. In addition, a similar analysis will be done for all AE and SAE that are possibly or probably attributable to the study intervention.

An event-based analysis will also be done since adverse events can be recurrent. In this analysis, a non-parametric method called the mean cumulative function (MCF)^{35,36} will be used as an alternative to the above crude incidence rate analyses. The overall safety profiles as well as the safety profiles in specific subgroups over the whole study period will be compared for the two randomization groups including the times of event recurrence and censoring mechanisms.

Time to event (survival analysis) will also compare the time to first MACE between treatment groups. A second survival analysis will be performed to identify risk predictors and to evaluate whether the observed treatment effect is modified by adjusting for covariates such as pre-existing CAD and pre-existing diabetes.

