## **Analysis of Secondary Effectiveness Outcomes**

The intent-to-treat principle will also be applied to all the secondary effectiveness outcomes analyses.

The change of %NC component of atheroma from baseline to 90-day follow-up will be analyzed using the two-sample t-test. The change scores for those who miss the 90-day follow-up assessment will be set to zero. Analysis of Covariance (ANCOVA) will be performed to evaluate the treatment effect on primary effectiveness outcome adjusting for age, pre-existing CAD, pre-existing diabetes, and baseline LDL levels.

The EPC-CFU/ml of peripheral blood assessed at 4 time points (pre-PCI, post-PCI, 30-day follow-up, and 90-day follow-up) will be analyzed via Mixed Linear models with random intercepts. The treatment effect, time effect and their interaction will be considered with or without adjusting for age, pre-existing CAD, pre-existing diabetes, baseline LDL levels, and other relevant covariates such as ACS, peripheral vascular disease, and chronic kidney disease. The statistical test of interest is the time by treatment interaction. Contrasts will be used in the Mixed Linear models to compare the differences among any specifically interested time points.

The incidence of major adverse cardiovascular endpoints (MACE) including death, myocardial infarction, coronary revascularization, and stroke will be analyzed in two ways. The percentage of people who experience the event at least once will be compared using the chi-square test. Logistic regression models will be performed to adjust for the covariates such as age, pre-existing CAD and pre-existing diabetes. An event-based analysis will also be done since MACE can be recurrent. In this analysis, a non-parametric method called the mean cumulative function (MCF) will be used as an alternative to the above crude incidence rate analyses. The overall safety profiles as well as the safety profiles in specific subgroups over the whole study period will be compared for the two randomization groups including the times of event recurrence and censoring mechanisms. Time to event (survival analysis) will also compare the time to first MACE between treatment groups. A second survival analysis will be performed to identify risk predictors and to evaluate whether the observed treatment effect is modified by adjusting for covariates such as pre-existing CAD and pre-existing diabetes.

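### The EPC mixed model gives each arm its own pre-PCI mean although that sample precedes randomisation; a common baseline mean would be a free gain in precision

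*Protocol*

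**What the plan says.** Protocol 1(c), item 5, states the objective as "The EPC-CFU/ml of peripheral blood, compared to SMT group from baseline to 30 days and 90 days post-PCI". For the analysis, Protocol 4(g)(v)(2) and the SAP (Analysis of Secondary Effectiveness Outcomes) list four times: pre-PCI, post-PCI, 30 days and 90 days. The values at these times "will be analyzed via Mixed Linear models with random intercepts". On the fixed effects the SAP says "The treatment effect, time effect and their interaction will be considered with or without adjusting for age, pre-existing CAD, pre-existing diabetes, baseline LDL levels", followed by an open-ended list of further covariates. Baseline LDL is named as a covariate; pre-PCI EPC is not. On testing it says "The statistical test of interest is the time by treatment interaction", and it adds "Contrasts will be used in the Mixed Linear models to compare the differences among any specifically interested time points".

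Protocol Table 1 places the first EPC sample before PCI. Randomisation comes later: once PCI and IVUS-VH are done, "the patients will be randomized to ILLT or SMT if they meet all inclusion and exclusion criteria" (Protocol 4(c)(i); 4(c)(v) agrees). Protocol 4(e) takes the pre-PCI level as the reference for all EPC analyses. The assay is confined to Dallas patients (Protocol 4(b) and 4(e); SAP, Secondary Effectiveness Outcome Measures). Neither document gives an SD, a within-patient correlation, an effect size or a power figure for EPC.

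**The concern.** Randomisation makes the true pre-PCI means equal in the two arms. A model with a free treatment effect and a free treatment-by-time interaction estimates a separate pre-PCI mean for each arm anyway. The 30- and 90-day contrasts then subtract the observed baseline difference with a coefficient of exactly 1, whatever the correlation between visits. The joint interaction test ignores the known baseline equality in the same way.

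Precision is at stake. EPC mobilisation is part of the trial's hypothesis, it is measured at one of four sites, and no power is claimed for it. Information already in the pre-PCI samples is worth using.

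**Working it through.** **Inputs from the documents.** Four EPC times; random intercepts; treatment, time and interaction; Dallas only; 1:1 allocation; 1.5 patients per site per month (Protocol 4(g)(iii)) over 22 months of enrolment.

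**Assumptions, because the documents are silent.** ρ, the correlation between the pre-PCI and a later value (0.3 to 0.7); k, the post/pre SD ratio (1 to 2); categorical time; complete data.

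**Patient number.** There is no stated EPC sample size to reproduce; the total of 128 was sized on the atheroma endpoint. For Dallas, 1.5 × 22 = 33, and 128/4 = 32 agrees. With 20% drop-out, 0.8 × 33 ≈ 26. Protocol 4(e) speaks of at least 50 assays; 33 patients × 4 samples = 132 assays would satisfy that. If patients were meant, it conflicts with the accrual figures. The variance ratios below do not depend on the number.

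**Step 1: what the planned contrast is.** The planned model and a common-baseline model were fitted to simulated data (17 vs 16 patients, four visits, 150 data sets at each ρ). The planned 90-day interaction estimate equalled the raw difference in mean change from pre-PCI to within 1e-14 in every data set.

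**Step 2: variance of one contrast.** In units of the pre-PCI variance, times a common factor for sample size:

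- planned: 1 + k² − 2ρk
- common baseline mean, or pre-PCI EPC as covariate: k²(1 − ρ²)
- planned minus adjusted: (1 − ρk)², which is never negative
- fraction saved: (1 − ρk)² / (1 + k² − 2ρk)

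At k = 1 the saving reduces to (1 − ρ)/2. Example with k = 1.25 and ρ = 0.5: planned 1 + 1.5625 − 1.25 = 1.3125; adjusted 1.5625 × 0.75 = 1.1719; saving 1 − 1.1719/1.3125 = 10.7%.

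| Variance saved | ρ = 0.3 | ρ = 0.5 | ρ = 0.7 |
|---|---|---|---|
| k = 1 | 35% | 25% | 15% |
| k = 1.25 | 22% | 11% | 2% |
| k = 1.5 | 13% | 4% | 0.2% |
| k = 2 | 4% | 0% | 7% |

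**Step 3: check by model fitting at k = 1.** Mean model SE of the 90-day contrast, planned vs common baseline: 0.407 vs 0.329 (ρ = 0.3), 0.347 vs 0.301 (0.5), 0.269 vs 0.248 (0.7). These agree with the k = 1 row: for example (0.301/0.347)² = 0.75.

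**Step 4: scale at k = 1.** At ρ = 0.5, 33 patients carry the information of 33/0.75 = 44 under the planned contrast. The difference detectable with 80% power falls from 0.98 to 0.84 SD.

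**Step 5: the named test.** With categorical time the interaction has 3 degrees of freedom. At k = 1 and compound symmetry, the covariance matrix of the three contrasts is proportional to (1 − ρ)(I + J) as planned and (1 − ρ)(I + ρJ) with a common baseline, where J is the 3 × 3 matrix of ones. Noncentrality per unit effect at ρ = 0.5:

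- effect at 90 days only: 0.75/0.5 = 1.5 planned, 0.8/0.5 = 1.6 with the fix, up about 7%
- equal effect at all three post-PCI visits: 0.75/0.5 = 1.5 planned, 1.2/0.5 = 2.4 with the fix, up 60%

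**The case against.** The strongest reply is that nothing here is invalid. The planned contrast is unbiased under randomisation, simulated type I error was about 5% with either analysis, and EPC is a secondary endpoint that Protocol 4(a) presents as initial evidence for later studies. All of that stands.

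The size of the gain is also uncertain. The 35%, 25% and 15% figures need equal SDs before and after. Protocol 2(a)(iv) cites 1.5-fold to three-fold rises in circulating EPC on statins in stable disease; if the spread grows with the mean, k exceeds 1 and the saving may be near zero. The guarantee of no loss is a large-sample one. In simulations at k = 1 with 17 vs 16 patients the savings were 32%, 23% and 12%, which is 2 to 3 points short of theory, so where ρk is close to 1 the fix is roughly neutral.

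A reader might infer four stronger things that the documents do not support:

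- *The planned test is simply a change-from-baseline comparison.* That is true of the single-visit contrasts. The named test is a joint one if time is categorical, and the coding of time is not stated.
- *A chance baseline imbalance passes in full into the estimated effect.* Given an imbalance D and k = 1, the contrast is off by (1 − ρ)D in size, which is 30% to 70% of D over this range of ρ.
- *This is the only EPC analysis.* There are adjusted and unadjusted models, contrasts, and complete-data and repeated-measures sensitivity analyses (Protocol 4(g)(ix); SAP, Handling Missing Data), and the SAP tabulates baseline EPC counts by arm. None of these writes in a baseline adjustment. The open covariate list could admit one, but it would not then be pre-specified.
- *The plan states 33 EPC patients.* It does not; the figure is derived from accrual.

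**Conclusion.** The point holds as a free improvement in efficiency for a secondary endpoint. It is not a finding of bias or of an invalid test. As written, the EPC model ignores the equality of arms before randomisation, so its 30- and 90-day contrasts are differences in mean change. In large samples they are never more precise than contrasts with a common baseline mean, and usually less.

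The variance saved on a contrast runs from nothing to about 35% over ρ = 0.3 to 0.7 and k = 1 to 2, with the larger savings at equal SDs and low correlation. The joint test gains about 7% to 60% in noncentrality at ρ = 0.5 and k = 1, depending on which visits carry the effect. ρ, k and the effect pattern are assumptions; the results also assume categorical time and complete data.

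**What to change.** In Protocol 4(g)(v)(2) and in the SAP's Analysis of Secondary Effectiveness Outcomes:

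1. State that time is categorical.
2. Replace the treatment main effect and full interaction with visit effects plus treatment-by-visit terms at the post-PCI, 30-day and 90-day times only, so that the pre-PCI mean is common to both arms (a constrained longitudinal model).
3. Prefer an unstructured covariance matrix, so that the result does not rely on equal variances.
4. Test the post-baseline treatment terms, and name the 30- and 90-day contrasts that match item 5 of Protocol 1(c).

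An alternative is to model the three later values with pre-PCI EPC-CFU/ml by visit as a covariate. Its small downside is that patients without a pre-PCI sample drop out unless that value is imputed; the constrained model keeps them.

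The cost is a change of wording. The pre-PCI sample is already scheduled, and because it precedes randomisation neither option conditions on anything the treatment could have affected.
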